3.6 Study Monitoring Procedures

3.6.1 Data and Safety Monitoring Board

An independent Data and Safety Monitoring Board will be established to monitor safety events in this study. Further details will be described in the Data and Safety Monitoring Board Charter.

3.6.2 Other Monitoring Committees

Not applicable.

4. Selection and Withdrawal of Subjects

4.1 Eligibility Criteria

The study population will be selected on the basis of the inclusion and exclusion criteria described in the sections below. Subject eligibility should be reviewed and documented by an appropriately medically qualified member of the investigator's study team before subjects are included in the study.

4.1.1 Inclusion Criteria

Subjects meeting all of the following inclusion criteria may be enrolled into the study:

1. Capable of providing informed consent/assent and willing and able to adhere to all protocol requirements. The subject's parent(s) or legally acceptable representative(s) capable of providing written informed consent.
2. Male or female on stable dose of IgPro20 (Hizentra) therapy.
3. Women of childbearing potential must be using and agree to continue using medically approved contraception (which must be discussed with the study doctor) and must have a negative pregnancy test at Screening.
4. Subjects with PID, eg, with a diagnosis of common variable immunodeficiency or X-linked agammaglobulinemia, as defined by the Pan American Group for Immune

Deficiency and the European Society of Immune Deficiencies or by the International Union of Immunological Societies Expert Committee.

5. With infusion parameters as specified below:

Pump-Assisted Flow Rate Cohort subjects only*

5a. Experience with pump-assisted infusions of IgPro20 at the tolerated flow rate of 25 mL/h** per injection site for at least 1 month prior to Day 1.

Pump-Assisted Volume Cohort subjects only*

5b. Total weekly IgPro20 dose of ≥ 50 mL (≥ 10 g).

5c. Experience with pump-assisted infusions of IgPro20 at tolerated volumes of 25 mL/injection site for at least 1 month prior to Day 1.

Manual Push Flow Rate Cohort subjects only

5d. Experience with frequent (2-7 times per week) infusions of IgPro20 at the tolerated flow rate of approximately 0.5 mL/min (equivalent of 25-30 mL/h) per injection site for at least 1 month prior to Day 1. The dose (volume) per injection site should not exceed 25 mL.

*Subjects who tolerated higher infusion parameters relevant for their study cohort prior to the study based on their chart records will not be allowed to participate in the study. If records are not available, information may be obtained by asking the subject.

**Subjects who use an infusion pump that operates by maintaining a constant pressure as opposed to a constant flow rate, may not have experienced flow rates that are exactly 25 mL/h. Flow rates for constant pressure pumps (adjusted for needle gauge and infusion tubing size) that are within $\pm 20\%$ of 25 mL/h per injection site are acceptable for study entry.

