1.1.4 SCIG Infusion Parameters

The currently approved Hizentra® infusion parameters in the United States (US) and abroad include a volume per injection site of up to 25 mL, and a flow rate of up to 25 mL/h per site (US package insert, European Union [EU] package insert), as outlined below:

Volume – For the first infusion of Hizentra, do not exceed a volume of 15 mL per injection site. The volume may be increased to 20 mL per site for the fifth infusion and then to 25 mL per site as tolerated.

Rate – For the first infusion of Hizentra, the recommended flow rate is 15 mL per hour per site. For subsequent infusions, the flow rate may be increased to 25 mL per hour per site as tolerated.

Higher infusion parameters, such as an increased flow rate and volume per injection site, reduce the time needed for infusion and decrease the number of injection sites, independent of the method used. An infusion of up to 60 mL per site and a flow rate of more than 60 mL/h using the manual push method have been previously described. In retrospective analyses of adult and pediatric patients using the rapid push method, the majority of subjects reported an infusion time of 9 minutes or less. With a mean volume per site of 15.8 mL in adults, an average flow rate of 1.75 mL/min or 105 mL/h can be assumed. In the age group of 10 to 18 years, an even higher flow rate of 1.9 mL/min (114 mL/h) can be assumed with a mean volume per site of 17.1 mL. Furthermore, in obese adults (body mass index [BMI] ≥ 30 kg/m²) a mean volume per site of 17.8 mL was documented, providing an average flow rate of 1.97 mL/min (118.67 mL/h) without tolerability issues (Shapiro 2013a; Shapiro 2013b; Shapiro 2013c).

While the flow rate in manual push is not usually presented in mL/h due to small volumes and short infusion times, a more detailed analysis of average flow rates, based on data from available publications, is presented in Table 1.

Table 1. Average Flow Rates in Manual Push Infusions

Manual push flow rate as originally reported	Flow rate, mL/min	Flow rate, mL/h	References
15 min per 3 mL	0.2	12	Berger, 2008.
1-2 cc/min	1-2	60-120	Misbah et al. 2009.
9 min per 15 mL	1.7	100	Shapiro, 2013b.
5 min per 10 mL	2	120	Richter et al., 2013.
9 min per 20 mL	2.2	133	Shapiro, 2013b.

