For pump-assisted infusions, higher infusion parameters have also been tested previously in clinical studies with IgPro20 (Hizentra). In the US PID extension study, IgPro20_3001, the protocol allowed for up to 40 mL per site and an infusion rate of up to 35 mL/h. In the EU PID pivotal study, ZLB06_001CR, the maximum infusion parameters allowed were 25 mL per site and 35 mL/h ([Jolles et al, 2015](#)). The same infusion parameters have been successfully tested in IgPro20 studies conducted in Japan ([Kanegane et al, 2014](#)). In all of these studies, there were no safety issues related to the higher injection site volumes or rates, although they were not evaluated in a systematic manner and there were not enough data collected to be able to draw robust conclusions. Additionally, in the recently completed IgPro20 study in subjects with chronic inflammatory demyelinating polyneuropathy, IgPro20_3003, injection site volumes and rates of 50 mL/site and 35 mL/h/site, respectively, were allowed. A substantial number of study subjects have already used these higher infusion parameters without safety issues.

In a recently published study of 20% SCIG administered to PID subjects in the US, the reported median infusion rate was 60 mL/h/site (range 4.4-180) and the median infusion volume per injection site was 39.50 mL (range 6.4-76.0), with 71.6% of subjects reaching a flow rate of at least 60 mL/h and 10.8% of subjects receiving a volume of at least 60 mL/site ([Suez Det al, 2016](#)). In the corresponding EU study, 41.6% of subjects reached a maximum infusion rate of ≥ 40 mL/h/site, with a number of study participants injecting 20% SCIG at 60 mL/h/site and with a volume of up to 48 mL/site ([Borte Met al, 2016](#)).

The above-mentioned publications, as well as numerous personal communications from immunologists treating PID patients demonstrate that, in current clinical practice, Hizentra infusions are sometimes conducted at significantly higher than currently approved flow rate and volume per injection site, with or without infusion pump (by manual push). The safety and tolerability of these new infusion parameters and techniques has not been evaluated in a systematic manner.

Therefore, the aim of this study is to obtain safety and tolerability data of higher infusion parameters of IgPro20 (Hizentra) in PID patients, for both pump-assisted and manual push techniques, allowing for greater flexibility and convenience of Hizentra infusions.

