2.1.2 Primary Endpoints

The primary endpoints are as follows:

- Pump-Assisted Volume Cohort: Percentage of responders for each planned volume (ie, 25 mL, 40 mL and 50 mL per injection site).
- Pump-Assisted Flow Rate Cohort: Percentage of responders for each planned flow rate (ie, 25 mL/h, 50 mL/h, 75 mL/h and 100 mL/h per injection site).
- Manual Push Flow Rate Cohort: Percentage of responders for each planned flow rate (ie, 30 mL/h [0.5 mL/min], 60 mL/h [1 mL/min], and 120 mL/h [2 mL/min] per injection site).

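### The bar on subjects who already tolerated higher infusion parameters covers both pump cohorts but not manual push, so that cohort's responder rates at 60 and 120 mL/h can be enriched by an unknown amount.

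*Protocol*

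**What the plan says.** Inclusion criterion 5 (protocol synopsis and section 4.1.1) sets entry conditions by cohort. The headings "Pump-Assisted Flow Rate Cohort subjects only" and "Pump-Assisted Volume Cohort subjects only" are each followed by an asterisk. The heading "Manual Push Flow Rate Cohort subjects only" is not, in either place. The asterisk leads to this note: "Subjects who tolerated higher infusion parameters relevant for their study cohort prior to the study based on their chart records will not be allowed" to take part. The note adds that, where records are missing, the subject may be asked.

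For manual push, criterion 5d requires experience with "infusions of IgPro20 at the tolerated flow rate of approximately 0.5 mL/min (equivalent of 25-30 mL/h) per injection site for at least 1 month" before Day 1. It caps the volume per site at 25 mL and sets no upper limit on flow rates tolerated at any earlier time.

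The levels tested in this cohort (section 2.1.2) are "30 mL/h [0.5 mL/min], 60 mL/h [1 mL/min], and 120 mL/h [2 mL/min] per injection site". A level succeeds if at least 33% of the cohort respond, which section 3.1 gives as 5 of 15. The highest successful level is to be recommended for the label (protocol 11.3.5, SAP 11.1). No formal test is planned.

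**The concern.** The stated aim is to learn whether patients can move up to parameters above those approved. The footnote serves that aim in the pump cohorts, because a subject who has already used the higher setting tells us little about a move up. The note refers to parameters relevant to each subject's own cohort, so its logic applies equally to manual push. Leaving that cohort out is unexplained.

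The protocol's background makes previous exposure plausible. Section 1.1.4 reports that volumes of up to 60 mL per site and "a flow rate of more than 60 mL/h using the manual push method have been previously described", and Table 1 lists published manual push rates from 12 to 133 mL/h. If some enrolled subjects had already tolerated 60 or 120 mL/h, part of the responder rate at those levels would restate known experience. With a threshold of 5 responders in 15, a few such subjects can change whether a level passes. Nothing planned in the SAP would show it: the subgroups are age and BMI only (SAP 8.2.9), and the highest rate previously tolerated is not among the baseline summaries (SAP 9.3).

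**Working it through.** **Step 1. Does any other rule close the gap?**

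| Place | Effect on a subject who once tolerated 60 or 120 mL/h by manual push |
|---|---|
| Criterion 5d | Needs at least 1 month at about 0.5 mL/min; does not look further back |
| Exclusion criteria, 4.1.2 | Previous flow rate not mentioned; number 13 is investigator discretion only |
| Section 6.2.1 | Limits parameters not under test to pre-study levels; flow rate is the parameter under test here |
| Section 6.1.2 | A subject who qualifies for more than one cohort is placed at the investigator's discretion |

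None of these bars such a subject. The marker is missing in both the synopsis and section 4.1.1, so loss of a character in text conversion is unlikely.

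**Step 2. Reproduce the plan's figure.** Protocol 11.1 gives 94% for an observed rate of at least 33% with n = 15 and a true rate of 50%. Since 4/15 = 26.7% and 5/15 = 33.3%, at least 5 responders are needed. P(X ≥ 5 | 15, 0.5) = 1 − 1941/32768 = 0.9408. The figure reproduces, and this point does not dispute it.

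**Step 3. Illustrate the possible enrichment.** Inputs from the documents: n = 15, at least 5 responders, planned rate 50%. Assumptions not in the documents:

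- a fraction f of subjects had already tolerated the level;
- those subjects always respond, which is an upper bound;
- the others respond at rate p.

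The mixed rate is q = f + (1 − f)p, and the chance of success is P(X ≥ 5 | 15, q). For example, f = 0.20 and p = 0.20 give q = 0.20 + 0.80 × 0.20 = 0.36 and a chance of 0.678.

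| Rate p in other subjects | f = 0% | f = 10% | f = 20% | f = 30% |
|---|---|---|---|---|
| 20% | q 0.20: 16% | q 0.28: 42% | q 0.36: 68% | q 0.44: 86% |
| 30% | q 0.30: 48% | q 0.37: 71% | q 0.44: 86% | q 0.51: 95% |
| 40% | q 0.40: 78% | q 0.46: 89% | q 0.52: 96% | q 0.58: 99% |
| 50% (planned) | q 0.50: 94% | q 0.55: 97% | q 0.60: 99% | q 0.65: 99.7% |

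**Step 4. Relax the upper bound.** Fix the number of previously tolerant subjects at 3 of 15 and let them respond at 90% or 100%. The chance of at least 5 responders is the sum over Binomial(3, 0.9 or 1.0) and Binomial(12, p):

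- p = 20%: 64% or 73%, against 16% with none
- p = 30%: 86% or 92%, against 48% with none
- p = 50%: 99% or 99.7%, against 94% with none

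The pattern is the same. The shift is large when the rate in other subjects is low and small at the planning assumption.

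**The case against.** Several counter-arguments have force.

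- **Partial protection exists.** A subject currently infusing at 1 to 2 mL/min does not fit 5d. The exposed group is people who tolerated a faster rate at some time and then spent at least a month near 0.5 mL/min. The documents give no indication of how many there are. This limits the problem but does not remove it.
- **Fast rates are not peculiar to manual push.** A reader might infer from Table 1 that previously tolerant subjects would be concentrated in this cohort. Section 1.1.4 does not support that. It cites a US study of 20% product with a median of 60 mL/h per site (range 4.4 to 180) in which 71.6% of subjects reached at least 60 mL/h, and it says practice exceeds approved settings with or without a pump.
- **Previous tolerance does not guarantee response.** A responder needs a minimum count of valid infusions, each within a duration limit and at 95% or more of planned volume, without prohibited medication (protocol 11.3.5, SAP 11.1). Section 1.4 mentions the manual strength needed and the difficulty of a stable flow. This is why the 100% response in Step 3 is only an upper bound.
- **Cohorts are not compared.** The primary endpoints are evaluated independently and no between-cohort safety comparison is planned. The issue is therefore how to read the manual push result itself.
- **The bar may not be the neutral standard.** It removes subjects known to tolerate more, but nothing removes those who tried more and failed, which could pull the pump cohorts' rates down. This stands, and it favours recording the history over excluding on it.

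**Conclusion.** The concern holds in a limited form. The eligibility rules treat manual push differently from the pump cohorts without a stated reason, and no other rule closes the gap. Responder rates at 60 and 120 mL/h in this cohort can therefore be enriched.

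The size is unknown. Under the assumptions in the working, with 10 to 30% of the cohort previously tolerant, the chance of meeting the criterion moves from 16% to 42–86% if the rate in other subjects is 20%, and only from 94% to 97–99.7% at the planned 50%. The gap matters mainly when the true rate is below the planning assumption, which is where the 33% rule has to discriminate.

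A reader might infer that the manual push result is in fact inflated, or that it would pass only because of selected subjects. The documents support neither reading: they do not show that any such subject was enrolled, and the 20% rate and the previously tolerant fractions are assumptions. This is an inexpensive improvement to interpretation and does not invalidate the endpoint.

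**What to change.** Record at Screening, for each manual push subject, the highest manual push flow rate previously tolerated. Take it from the chart, or ask the subject, as the footnote already allows for the pump cohorts. Keep R_c,p on the full Safety Population as planned. Add one supportive row at 60 mL/h and one at 120 mL/h that leaves out of both numerator and denominator the subjects who had already tolerated that level. If enrolment is complete, the same information can be sought from charts.

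Alternatively, extend the existing footnote to the manual push heading in both the synopsis and section 4.1.1 if recruitment allows, or state why this cohort is treated differently.

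The cost of recording is one eCRF field and an extra table row per level. That row has a smaller denominator: with 3 of 15 left out, each subject counts 100/12 = 8.3 percentage points instead of 100/15 = 6.7. Some histories will rest on recall. Extending the footnote would shrink the recruitment pool by an amount the documents do not let us judge.

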4.1.2 Exclusion Criteria

Subjects meeting any of the following exclusion criteria must not be enrolled into the study:

1. Ongoing SBI at the time of Screening. Serious bacterial infections as defined by [FDA Guidance \(2008\)](#).
2. Other significant medical conditions that could increase the risk to the subject.
3. Females who are pregnant, breast feeding, or planning a pregnancy during the course of the study.
4. Participation in a study with an Investigational Medicinal Product (IMP) other than IgPro20 within three months prior to enrollment.

5. Evidence of uncooperative attitude or unable to complete scheduled visits for any reason.
6. Any condition that is likely to interfere with evaluation of the IMP or satisfactory conduct of the study.
7. Subjects who are employees at the investigational study site, or relatives or spouse of the investigator.
8. Female subject of childbearing potential either not using or not willing to use a medically reliable method of contraception or not sexually abstinent during the study, or not surgically sterile.
9. Alcohol, drug or medication abuse within 1 year before the study.
10. Currently receiving a therapy not permitted during the study, as defined in [Section 7.3](#).
11. Mental condition rendering the subject (or the subject's legally acceptable representative[s]) unable to understand the nature, scope and possible consequences of the study.
12. Known or suspected hypersensitivity to IgPro20, or to any excipients of IgPro20.
13. Any issue that, in the opinion of the investigator, would render the subject unsuitable for participation in the study.

4.2 Subject Withdrawal

4.2.1 Subject Withdrawal

Subjects may withdraw from the study at any time at their own request, or they may be withdrawn at any time at the discretion of the investigator or CSL for safety, behavioral or administrative reasons (eg, due to an AE, protocol deviation, loss to follow-up, subject noncompliance, and study termination).

In accordance with International Conference on Harmonisation (ICH) principles of Good Clinical Practice (GCP) the investigator always has the option to advise a subject to withdraw from the study if the subject's safety or well-being is compromised by his or her further participation in the study. Concern for the interests of the subject must always prevail over the interests of the study.

If a subject is withdrawn from the study or further participation is declined, they will continue to have access to medical care and will be treated as per routine medical practice.

4.2.2 Procedures for Handling Withdrawals

If a subject declines further participation or is withdrawn from the study, attempts will be made to complete and document the final assessment. If the subject is withdrawn from the study after receiving IgPro20, every effort will be made to ensure that the relevant safety assessments are completed. The subject may also be asked by the investigator to complete other study assessments.

If the subject withdraws from the study, and also withdraws consent for disclosure of future information, CSL may retain and continue to use any data collected before such withdrawal of consent.

In the event that a subject withdraws from the study, the investigator should record the reason and date of withdrawal in the electronic case report form (eCRF) and in the subject's medical records.

4.2.3 Replacement Policy

Subjects withdrawn from the study will not be replaced.

5. Study Interventions

5.1 Description of Investigational MEDICINAL Product

5.1.1 IgPro20

Substance number	IgPro20
Active substance	Human normal immunoglobulin
Trade name	Hizentra
Dosage form	Solution for SC injection (ready-to-use formulation of polyvalent SCIG)
Dose	As prescribed by subject's healthcare provider prior to study entry, usually within 100-200 mg/kg per week range.
Mode of administration	SC

SC=subcutaneous.

The study IMP, IgPro20, will be manufactured by CSL in accordance with Good Manufacturing Practice guidelines and local regulatory requirements, and will be labelled as the IMP for this study.

5.1.2 Comparator Product

Not applicable.

5.2 Packaging, Labeling, Supply and Storage

5.2.1 Packaging and Labeling

IgPro20 will be packaged and labeled according to current ICH Good Manufacturing Practice and GCP guidelines, and national legal requirements.

5.2.2 Supply and Storage

IgPro20 will be supplied to the study sites by external service providers on behalf of CSL. IgPro20 must be stored between 2°C and 25°C (36°F and 77°F) and protected from light, in a secure storage area as specified in the IMP Handling Instructions.

5.3 Accountability and Destruction

All supplies of IgPro20 must be accounted for throughout the study. At the end of the study, the original IMP Inventory Log, dated and signed by the investigator or delegate (eg, pharmacist), must be retained at the study site as verification of final accountability of IgPro20.

Records for the delivery of IgPro20 to the study site, the inventory at the study site, the use by each subject, and the destruction or return of IgPro20 to CSL's external service providers must be maintained by the investigator (or delegate). The records will include dates, quantities, lot numbers, kit numbers and unique code numbers assigned to IgPro20 and assigned to the subjects. The investigator must provide reasons for any discrepancies in IMP accountability.

Information on the destruction of IgPro20 is provided in the IMP Handling Instructions / Pharmacy Manual.

5.4 Other Intervention(s)

Not applicable.

5.5 Rescue Therapy

Not applicable.

6. Allocation, Dosing and Administration

6.1 Allocation to Treatment

6.1.1 Subject Assignment

After providing written informed consent, the subject will be issued with a study-level unique subject identification number. The subject identification number will be used to identify the subject for the duration of the study. Subject identification numbers will not be reassigned or reused.

6.1.2 Randomization Procedures

Each study cohort requires specific entry criteria ([Section 4.1.1](#)). However, these criteria are not mutually exclusive, and if a subject qualifies to be enrolled into more than 1 of the study cohorts, he/she may be assigned to either cohort at the investigator's discretion.

6.1.3 Blinding Procedures

Not applicable.

6.2 Dosing and Administration

6.2.1 Dosing and Administration

IgPro20 will only be administered by subjects included in this study following the procedures set out in this study protocol. An Interactive Response Technology (IRT) system will be utilized during the study for IMP accountability.

Enrolled subjects will administer SC IgPro20 at a dose prescribed by their healthcare provider prior to study entry (usually 100-200 mg/kg per week). Subjects in the Pump-Assisted Cohorts will administer weekly treatment and subjects in the Manual Push Cohort will administer frequent infusions (ie, 2-7 times per week). Subjects in the Manual Push Cohort should maintain the same frequency of infusions per week throughout the whole

study, including 1 month prior to Day 1. The infusion parameters not under test (eg, volume per injection site in the flow rate cohort) should not exceed the levels used before the study.

IgPro20 can be stored at room temperature between 2°C and 25°C (36°F and 77°F), protected from light. The IMP should be at room temperature before use. The IMP should not be shaken. Excessive shaking will cause foaming. For a more detailed description of the preparation of the IMP, refer to the handling instructions in the Subject IMP Handling Guide.

